#### **6.9 Measures**

*Study measures are described below. Based on PedIMMPACT guidelines, the primary treatment outcomes will be pain interference, pain characteristics (burden, intensity, frequency), and pain coping efficacy. Secondary outcomes will include healthcare use for pain (admissions, ED visits, opioid use). Questionnaires will be completed online using REDCap or paper-and-pencil, depending on*

*participant preference. Children and their parents will complete their questionnaires separately. The total time for the full battery of child and parent questionnaires is approximately 20 minutes. We will monitor changes in medical or psychiatric treatment during the study through medical chart review.*

#### **6.10 Treatment Feasibility**

- 1) Study recruitment and enrollment statistics*
- 2) Treatment adherence as demonstrated by drop-out rate, session completion, missed/rescheduled treatment sessions, therapist ratings of participants' homework completion*
- 3) Completion of study assessments*
- 4) Participant ratings on whether they thought the Back2Life program is a reasonable approach for chronic pain management, if the program was helpful, could be integrated into their lifestyle, and description of barriers in implementing the program.*

#### **6.11 Treatment Acceptability**

*Treatment Evaluation Inventory, Short Form will be completed at immediate post-treatment. It includes 9 items adapted to be specific to pediatric pain. Items are rated on a 5-point Likert scale ranging from 1 to 5. Total scores range from 9-45. Scores ≥ 27 indicate "moderate" treatment acceptability30.*

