## 2.0 Objectives\*

**2.1 Primary Aim:** Conduct a pilot proof-of-concept clinical trial to evaluate the feasibility, acceptability, and preliminary efficacy of Back2Life with youth with chronic SCD pain and their parents (n=25). We will use an adaptive treatment approach with 6-10 module-based treatment sessions selected on the

basis of baseline assessment (rather than a fixed treatment approach) to allow flexibility in tailoring treatment components to meet individual family needs.

*2.2 Hypothesis 1: It is expected that the Back2Life treatment program will be feasible and acceptable as demonstrated by high levels of treatment engagement ( $\geq 80\%$  attendance of treatment sessions) and high ratings of treatment satisfaction.*

*2.3 Hypothesis 2: Participants who complete the Back2Life treatment program will report reductions in pain interference and pain symptoms (intensity and frequency) at post-treatment and 6-month follow-up. Preliminary efficacy will be defined as clinically significant ( $\geq 30\%$ ) reductions in pain interference and pain.*

*2.4 Exploratory hypothesis 1: We will explore reductions in secondary outcomes related to healthcare use for pain (inpatient hospitalizations, ED visits, and opioid use) at 6-month follow-up.*

*2.5 Exploratory hypothesis 2: The Back2Life treatment program will result in measurable reductions in inflammatory biomarkers from baseline to 3-month and 6-month follow-up.*

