**6.5 Follow-Up Assessments:** All teens and parents will complete the same assessment of surveys after completing the standard 6-session program (post-treatment evaluation). Parents will also report on any changes to their teen's medical treatment plan since the last assessment. All teens and parents will

*complete the assessments at 3-months and 6-months follow-up from baseline. All assessments can be completed in-person, at home using online or paper-and-pencil questionnaires, or by telehealth (video or phone) depending on teen and parent preference. An assessment window of +/- 2 weeks will allow flexibility to support recruitment and adherence.*

**6.6 Blood Sample Collection:** *As an optional component of the study, all teens will have the option to consent to blood sample collection at three assessment visits: baseline, 3-month follow, and 6-month follow-up. Blood sample collection will occur at or close to each time point allowing at least 2 weeks following an acute care visit for pain to ensure steady disease state collection. To enhance clinical implementation and acceptability, efforts will be made to coordinate blood sample collection during routine medical visits to minimize blood draws. Each sample will be about 4 teaspoons (about 20 milliliters) of blood, which will be drawn in the clinic or hospital, and will only take a few seconds. Collected blood samples will be immediately transported to [name] laboratory for labeling, processing, storage, and analysis.*

**6.7 Qualitative Interview:** *At the end of the treatment program, parents and teens will be asked for feedback in a one-on-one interview lasting about 30 minutes. Feedback may include how they liked the program, what they thought about the content of the program, and any suggestions or changes to the materials or format. Information from these interviews will be used to refine and modify the Back2Life program. Interviews can be conducted in-person or by telehealth (video and/or phone). Interviews will be audio recorded as digital files and transcribed for analysis by advanced psychology PhD students or trained study members. Audio recordings will be saved for up to 6 years following completion of the study and saved via password-protected computer that is only accessible to the PI to ensure security. No audio recordings will be used for educational or presentation purposes. The research design does not require subjects to be deceived.*

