## **14.0 Withdrawal of Participants\***

- 14.1** Participants have the right to leave the study at any time without penalty. If participants choose to go off the study treatment or leave the study before the final planned study visit, participants may be asked to have some final study procedures completed including but not limited to follow-up surveys at the planned end of the program, and follow-up surveys at 3-months and 6-months after the program.
- 14.2** Study personnel may stop participant involvement in the study without participant consent for any reason to maintain the best interest of the participant or if participants object to any future changes that may be made in the study plan.

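### Acceptability is scored once, after the program, and collecting it from families who leave is optional, so the result will rest mainly on completers

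*Combined protocol and SAP*

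**What the plan says.** Section 4.1 lists acceptability among the primary endpoints. Hypothesis 1 in 2.2 ties feasibility and acceptability to at least 80% "attendance of treatment sessions) and high ratings of treatment satisfaction". Attendance gets a number there and satisfaction does not.

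On the instrument, 6.11 states: "It includes 9 items adapted to be specific to pediatric pain" and "Items are rated on a 5-point Likert scale ranging from 1 to 5. Total scores range from 9-45". It gives one interpretive line, a total of at least 27, labeled moderate and attributed to a cited source. It gives no verbal anchors for the five response points and does not say whether teens, parents or both complete the form.

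On timing, 6.11 says "Treatment Evaluation Inventory, Short Form will be completed at immediate post-treatment". Section 6.5 places that evaluation at the point where participants "complete the same assessment of surveys after completing the standard 6-session program (post-treatment evaluation".

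For those who leave, 14.1 says "participants may be asked to have some final study procedures completed including but not limited to follow-up surveys at the planned end of the program". The TEI-SF is not mentioned.

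Section 17.3 says acceptability will be assessed with the TEI-SF and qualitative interviews, with no target, denominator or rule for non-response. Section 17.1 has one general sentence committing to multiple imputation or maximum likelihood for missing data.

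**The concern.** Families who stop coming because the program did not suit them are the ones whose opinion matters most for acceptability, and they are the ones this schedule is most likely to miss. The second source, the interview in 6.7, also takes place at the end of the program, so it does not fill the gap.

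What is at stake is the decision described in 5.0: whether the treatment merits a randomized trial or needs further optimization. An acceptability figure drawn mainly from those who stayed favors the first answer. With 25 dyads, a handful of missing families can move the figure a long way.

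**Working it through.** **Inputs.** Nine items scored 1 to 5, total 9 to 45, line at 27 (6.11). Enrollment of 25 dyads (1.0, 12.1). One administration, immediately post-treatment (6.11, 6.5). Dropout is not stated anywhere, so 10% to 40% is assumed. In whole families out of 25 this is taken as 2, 5, 8 and 10 leavers (8%, 20%, 32% and 40%).

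**Step 1: reproduce the scale.** Minimum 9 × 1 = 9; maximum 9 × 5 = 45. This matches 6.11. The midpoint is (9 + 45)/2 = 27 = 9 × 3, so the line sits at (27 − 9)/(45 − 9) = 50% of the range. A mean item score of 4 would total 9 × 4 = 36.

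**Step 2: can the missing-data sentence repair the gap?** The form is given once, so a family without a post-treatment form has no TEI-SF score at any time. Imputation or likelihood methods would have to predict it from other variables (baseline measures, attendance, homework), using relations estimated in those who did respond. If leaving itself reflects dissatisfaction, those relations do not carry over.

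**Step 3: size of the effect.** Let N = 25 enrolled, n respondents, and x respondents at or above the line. The respondent rate is x/n. Counting missing as not acceptable gives x/N. Counting missing as acceptable gives (x + N − n)/N. Intervals are exact (Clopper-Pearson) 95%.

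Case A, every respondent at or above the line (x = n):

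| Leavers | Among respondents | All enrolled, missing = not acceptable |
|---|---|---|
| 2 | 23/23 = 100% (85 to 100) | 23/25 = 92% (74 to 99) |
| 5 | 20/20 = 100% (83 to 100) | 20/25 = 80% (59 to 93) |
| 8 | 17/17 = 100% (80 to 100) | 17/25 = 68% (46 to 85) |
| 10 | 15/15 = 100% (78 to 100) | 15/25 = 60% (39 to 79) |

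Case B, about 80% of respondents at or above the line:

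| Leavers | Among respondents | Lower bound x/N | Upper bound (x + N − n)/N |
|---|---|---|---|
| 2 | 18/23 = 78% | 18/25 = 72% | 20/25 = 80% |
| 5 | 16/20 = 80% | 16/25 = 64% | 21/25 = 84% |
| 8 | 14/17 = 82% | 14/25 = 56% | 22/25 = 88% |
| 10 | 12/15 = 80% | 12/25 = 48% | 22/25 = 88% |

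In Case A the respondent figure stays at 100% however many leave, while the lower bound falls by 8 to 40 percentage points. Case B shows that the room for error is mostly downward: with 5 leavers it is 16 points down and 4 points up.

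**The case against.** The protocol is not silent about people who leave. Section 14.1 expressly allows surveys at the planned end of the program. Section 17.2 reports dropout, session completion and the proportion completing assessments, so a reader would see the attrition. Acceptability also draws on interviews (17.3), and 17.2 adds participant ratings of whether the program is reasonable and helpful. Section 17.1 requires means, standard deviations and ranges for all measures, so a mean near 27 would be visible. The dropout figures above are assumed.

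All of that stands, and it rules out three stronger readings that a reader might infer.

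- *That the scale is measured only in those who reach the end of treatment.* It is scheduled only then, but 14.1 permits collection from leavers. A respondent-only result is a risk, not a stated plan.
- *That 27 is the plan's pass mark and is met by indifference.* Neither 2.2 nor 17.3 uses 27 as a success criterion, and 6.11 itself calls it moderate. Without verbal anchors, 27 can be called the midpoint but not a neutral opinion.
- *That a favorable conclusion would follow whatever families think.* A respondent averaging 2 per item totals 9 × 2 = 18 and falls well short of 27, and the interviews and other ratings could also point the other way.

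What the objection does not answer is that collection from leavers is optional and does not name the TEI-SF, that no denominator is set, and that the interviews share the same timing. Reporting dropout beside the acceptability figure helps a careful reader but does not correct the figure.

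**Conclusion.** The point holds as a matter of non-response. With one administration after the program, optional collection from leavers and no earlier score to impute from, the acceptability result will rest mainly on completers. For 2 to 10 leavers of 25, a respondent rate of 100% is compatible with a worst-case all-enrolled rate of 92% down to 60%.

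Two assumptions carry this. The dropout range is illustrative, because the documents give none. The direction, too favorable, assumes that leavers are on average less satisfied; if they leave for unrelated reasons the bias is small, and the lower bound is then only a bound.

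On the threshold, the supported conclusion is limited: Hypothesis 1 predicts high satisfaction and no number defines high. That is missing detail, not a wrong criterion. It does mean that reaching 27 cannot by itself be offered as support for the hypothesis.

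For an uncontrolled pilot this is an inexpensive improvement worth making, not a flaw that invalidates the design.

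**What to change.** - **6.11 and 14.1:** name the TEI-SF and offer the nine items to every participant at the time of withdrawal, as well as at post-treatment. Completion stays voluntary.
- **17.3:** report the proportion at or above the chosen line for teens and parents separately (6.9 has them complete questionnaires separately), each with an exact 95% confidence interval. Give it among respondents and, as a sensitivity bound, over all enrolled with non-responders counted as not acceptable. Use enrolled parents as the parent denominator, since 10.3 lets 18-year-olds join without one.
- **2.2 and 17.3:** do not present a total of 27 as evidence of high satisfaction. If the sponsor wants a line for high, fix it in advance. A total of 36 (mean item score 4) is one option, but it has no basis in the documents and the choice is the sponsor's.

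The cost is a few sentences of protocol text and a short form for the few who withdraw. The reported figure may be less favorable.

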#### **6.12 Primary Treatment Outcomes**

- 1) PROMIS Pediatric Short Form-Pain Interference, Self- and Parent-Proxy Report is an 8-item self-report measure that will assess functional interference due to pain in the past 7 days. PROMIS Pediatric measures have been well validated among youth with SCD and chronic pain in inpatient and outpatient settings31-34. (2-3 mins)*
- 2) Sickle Cell Pain Burden Interview for Youth, Self-Proxy Report is a brief, validated measure of pain burden in 7-21 year olds. It demonstrated strong reliability and validity among youth with SCD from inpatient and outpatient settings35. Patient self-report and parent-proxy report of total pain days in the past month and duration of chronic pain will also quantify pain frequency1,35. (2-3 min)*
- 3) PROMIS Pediatric Short Form-Pain Behaviors, Parent-Proxy Report is an 8-item measure completed by parents that assesses pain behaviors displayed by their child in the past 7 days. PROMIS Pediatric measures have been well validated among youth with SCD in inpatient and outpatient settings (2-3 min)*

4) *Child Self-Efficacy Scale, Self- and Parent-Proxy Report* is a well-established, 7-item measure of self-efficacy for functioning despite pain for 8-19 year olds. It demonstrated good internal consistency and validity among youth with a variety of pain problems. (2-3 min)

#### 6.13 Secondary Treatment Outcomes

1) *Healthcare utilization will be extracted from the medical record to document the total number of emergency department (ED) visits and admissions for pain for 6-months and 12-months pre- and post-treatment.*

2) *Opioid use will be calculated based on participant completion of daily diaries for 1-week at each assessment visit. Participants will record opioid use daily (presence/absence). Opioid use also will be documented on daily diaries throughout the course of treatment.*

3) *Inflammatory biomarkers, including but not limited to, proinflammatory cytokines and markers, such as interleukin -18 (IL-18), interleukin – 6 (IL-6), interleukin – 8 (IL-8), tumor necrosis factor – alpha (TNF- $\alpha$ ), c-reactive protein (CRP), brain-derived neurotrophic factor (BDNP), and interferon gamma (INF- $\gamma$ ) will be analyzed. Plasma concentrations for each biomarker will be determined by a custom multiplex kit (e.g., FirePlex-384 Multiplex Assay by abcam), an immunoassay panel detected by flow cytometry used for simultaneous quantitative measurement in a single sample with high sensitivity and high throughput capacity. All samples will be analyzed in triplicate.*

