## 1.0 Study Summary

Study Title	Building Adaptive Coping and Knowledge to Improve Daily Life (Back2Life): A Pilot Feasibility Clinical Trial for Youth with Chronic Sickle Cell Pain
Study Design	Single-Arm, Uncontrolled Behavioral Clinical Trial
Primary Objective	Conduct a pilot proof-of-concept clinical trial to evaluate the feasibility, acceptability, and preliminary efficacy of Back2Life with youth with chronic SCD pain and their parents
Secondary Objective(s)	Refine intervention content and delivery based on participant qualitative feedback; Evaluate a biological response to intervention
Research Intervention(s)/Interactions	The treatment program includes 6-sessions of standard cognitive-behavioral therapy (CBT) treatment (delivered to all participants) and 1-4 tailored sessions to address common co-morbidities associated with chronic pain (sessions assigned based on results of baseline assessment). The treatment manual leverages existing evidence-based interventions into a treatment package that will be tailored to individual patient and family needs.
Study Population	Children with sickle cell disease (SCD) aged 10-18 years old and their parent(s)
Sample Size	25 parent-child dyads
Study Duration for individual participants	8 months
Study Specific Abbreviations/ Definitions	Back2Life: Building Adaptive Coping and Knowledge To improve daily Life CBT: cognitive-behavioral therapy
Funding Source (if any)	NHLBI

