**6.4 Treatment Sessions:** The treatment sessions will be conducted in-person at a CHOA hospital campus or via telehealth using HIPPA-compliant platform (e.g., Zoom). An in-person study visit for the first treatment session is strongly encouraged to promote optimal therapeutic rapport, and all remaining treatment sessions may be conducted in-person or via telehealth, based on patient/family preference. Treatment sessions will begin 1 week following the completion of baseline assessment. Each session will last about 1 hour, once a week. A treatment session window of +/- 14 days will allow flexibility to support adherence. Each session will focus on teaching a new skill or strategy to improve chronic pain management. Sessions will be led by a psychology provider (PhD student, post-doctoral fellow, psychologist). Teens will be asked to practice the coping skills at home between sessions and keep a brief diary of their practice, pain symptoms, school attendance, and medication use. At least one parent or guardian is required to attend with their teen. However, all interested family members (parents, grandparents, siblings) are encouraged to attend sessions with their teen. Parents will also receive education and training in the skills their teen will be learning along with behavior management strategies to support teen's use of skills at home. One booster session will be offered 2 months after completing the program. The booster session will focus on problem-solving any difficulties teens or parents may have had with using the skills at home or school. The booster session will be conducted either in-person, telehealth, or by phone, depending on family preference. Intervention content will be sensitive to developmental differences. For example, parents of school-aged children will be guided to coach their children's use of coping strategies. Parents of adolescents will be guided to provide monitoring and oversight of adolescent self-management and communication with providers to promote independence. Sessions may be audio recorded and will only be reviewed by research staff to make sure that the content of the training program is being provided accurately and thoroughly to all participants. Between sessions, follow-up by phone or during inpatient admissions will allow for opportunities to problem-solve integration of strategies. Make-up sessions will be built into the treatment session timeline to allow flexibility and treatment adherence.

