## **13.0 Recruitment Methods**

*13.1 Eligible patients will be identified for the study from new or existing SCD patients being seen through the CHOA Comprehensive Sickle Cell Program. We will use multiple recruitment strategies used in past studies. Describe the source of participants.*

*13.2 Participants in our research database who have agreed to be contacted for future studies will be contacted with a letter describing the study in a “who, what, where, and why” format and/or a personal phone call to the family to describe the study in further detail and determine interest and eligibility. Patients and parents expressing interest in the study will be provided the option to complete web-based or paper baseline measures at home, during their next scheduled outpatient clinic appointment, or during/following their inpatient admission. Verbal consent with the parent will be completed over the phone for participants from the existing study cohort. The research team will call participants to follow-up about baseline survey completion.*

*13.3 Second, all eligible patients will be approached and screened during their routine outpatient SCD appointment or inpatient admission. Parents or legal guardians of patients must provide written consent for their child to be eligible for inclusion, and youth will provide written assent. Parents will be invited to participate as well and must provide written consent for their own participation. How will eligibility be determined? Provide a detailed description of any eligibility screening done prior to enrolling subject (including whether any identifiers will be recorded – note that IP address is an identifier)*

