and a coding scheme will be developed. Qualitative data will be analyzed using MAXQDA. Interview data will be coded by two independent reviewers to enhance confirmability and dependability of conceptual domains. Describe the steps that will be taken to secure the data (e.g., training, authorization of access, password protection, encryption, physical controls, certificates of confidentiality, and separation of identifiers and data) during storage, use, and transmission.

**17.4** Preliminary efficacy will be examined by calculating standard effect sizes and 95% confidence intervals on primary outcomes (pain interference, pain, coping) at post-treatment and 3- and 6-month follow-up. Changes in primary outcomes over time will be assessed using repeated measures ANOVA. Comparisons between time points will be made using paired tests or Wilcoxon tests. In an adjusted analysis, potential control covariates (e.g., child age, number of sessions, changes in treatment) will be examined as appropriate. Based on past CBT pain trials, pain reductions typically occur from baseline to follow-up and independent of changes in pain interference. To account for potential non-significant changes in pain intensity, we will examine individual clinically significant ( $\geq 30\%$ ) reductions in pain and interference.

**17.5** Power Analysis: We are not attempting to fully power this proof-of-concept study and will only examine preliminary efficacy using exploratory analyses. Preliminary power analyses were based on meta-analysis of CBT for pediatric chronic pain. We estimate an effect size of  $d=.55$  for pain reduction at follow-up (30% pain reduction). A sample size of  $n=25$  would achieve power estimates of approximately 80%.

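### Pre-treatment counts of pain admissions and ED visits include the event at which a teen was recruited, which biases the pre/post change in healthcare use towards a reduction

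*Combined protocol and SAP*

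**What the plan says.** Healthcare use is a secondary outcome taken from the chart. Section 6.13 says "Healthcare utilization will be extracted from the medical record to document the total number of emergency department (ED) visits and admissions for pain", and the same sentence sets the windows: "admissions for pain for 6-months and 12-months pre- and post-treatment". It does not say on which day the pre-treatment window ends, and it does not set aside the admission or visit at which a family was recruited.

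On recruitment, section 13.3 says that "all eligible patients will be approached and screened during their routine outpatient SCD appointment or inpatient admission". Section 13.2 adds letter and phone contact with families in the research database, who may complete baseline measures at home, "during their next scheduled outpatient clinic appointment, or during/following their inpatient admission". Section 13.4 adds letter and phone contact after a missed clinic appointment. No share is given for any route.

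On timing, section 6.4 says "Treatment sessions will begin 1 week following the completion of baseline assessment".

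The design is a "Single-Arm, Uncontrolled Behavioral Clinical Trial" (section 1.0). Section 2.4 gives the purpose of the outcome: "We will explore reductions in secondary outcomes related to healthcare use for pain", at 6-month follow-up. Section 17.4 ties its analyses to the primary outcomes and names none for healthcare use. Its adjusted analysis says "potential control covariates (e.g., child age, number of sessions, changes in treatment) will be examined as appropriate"; recruitment setting is not among the examples.

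**The concern.** The comparator for healthcare use is each teen's own recent past. If a teen enters the trial because a pain admission put the family in front of the study team, the pre-treatment window holds at least one event by selection. The post-treatment window carries no such condition. A concurrent control arm recruited in the same way would show the same pattern and reveal it. This trial has none.

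The short interval between baseline and the first session keeps the recruiting admission inside both the 6- and the 12-month window, unless baseline is long delayed. The gap after acute care in section 6.6 does not help, since it governs blood samples only. A similar gap before the questionnaires would not help either, because this outcome is a retrospective chart count.

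At stake is how a fall in admissions or ED visits is read. Section 5.0 says the trial should show whether the treatment merits a randomised trial. As planned, part of any fall could reflect where families were recruited, and the data would not show how much.

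**Working it through.** **The plan's own figure.** There is none for healthcare use. The power statement in section 17.5 concerns pain reduction and has no bearing here.

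**Inputs from the documents.** 25 dyads (section 12.1); windows of 6 and 12 months on each side of treatment (6.13); recruitment during admissions allowed (13.3); first session 1 week after baseline (6.4); no control arm (1.0).

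**Assumed inputs.** k of the 25 teens are recruited during a pain admission, so f = k/25. The mean rate is the number of pain admissions per window, not counting the recruiting one. Treatment has no effect and each teen's rate is the same before and after. The pre-treatment window is taken to run up to the start of treatment.

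**Expected counts per teen.**
- Before: rate + f
- After: rate
- Expected apparent fall: f/(rate + f)

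Teens may differ in their rates; the formula needs only the cohort mean.

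**Numbers put in.**
- k = 3, rate 4 per 6 months: 0.12/4.12 = 2.9%
- k = 8, rate 1 per 6 months: 0.32/1.32 = 24.2%
- k = 8, rate 0.5 per 6 months: 0.32/0.82 = 39.0%
- k = 8, 12-month window at the same underlying rate as the second case (2 per 12 months): 0.32/2.32 = 13.8%

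Expected 6-month fall for the whole cohort, with no treatment effect:

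| Rate per 6 months | k = 3 | k = 5 | k = 8 | k = 13 |
|---|---|---|---|---|
| 0.5 | 19.4% | 28.6% | 39.0% | 51.0% |
| 1 | 10.7% | 16.7% | 24.2% | 34.2% |
| 2 | 5.7% | 9.1% | 13.8% | 20.6% |
| 4 | 2.9% | 4.8% | 7.4% | 11.5% |

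The same formula applies to ED visits, with f as the share whose recruiting event included an ED visit for pain and the ED visit rate in place of the admission rate.

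**Effect on a test.** This was simulated with 20,000 trials of 25 teens, Poisson counts with gamma-distributed rates (shape 1), and a paired t-test at two-sided 0.05. The plan names no test for this outcome, so the t-test is an assumption. At rate 1 and k = 8, the cohort total fell in 86% of trials with no treatment effect, and the fall was significant in 18.0%, against a nominal 2.5% in that direction. At rate 1 and k = 3, it was significant in 5.6%. With no recruiting event in the count (k = 0), the expected fall is 0% and the simulated rate of a significant fall was 2.4%.

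**The case against.** Five points can fairly be made against the concern.

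1. **Admissions need not be for pain.** Section 13.3 refers to inpatient admissions in general, while 6.13 counts those for pain. An admission for another reason adds nothing. No passage says that admissions come through the ED, so a linked ED visit is only a possibility. This stands, and it is why f is defined by pain admissions.

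2. **The ward is one route among several.** Outpatient clinics, database contacts and families who missed appointments are the others. If few teens come from the ward, the bias is small: with one teen and rate 1 it is 0.04/1.04 = 3.8%. This stands too. The plan offers no basis for choosing k.

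3. **The fall is not guaranteed.** A reader might infer that visits must drop after treatment by construction. The documents do not support that. The bias is in the expected change only. Even at rate 1 and k = 8, about 14% of simulated null trials showed no fall in the total.

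4. **The outcome is exploratory.** Section 17.5 disclaims full power, no decision threshold rests on healthcare use, and feasibility, acceptability and the primary outcomes do not use the count. This limits the consequence. It does not remove the bias from a figure whose purpose is to look for reductions.

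5. **The 12-month window dilutes the effect.** It does, from 24% to 14% in the middle case, but it does not remove it.

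None of these points to a rule that keeps the recruiting event out of the count.

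**Conclusion.** The concern holds in a limited form. For any teen recruited during a pain admission, the plan as written puts the recruiting event in the pre-treatment count and has nothing to balance it afterwards. The expected change in healthcare use is therefore biased towards a reduction even when treatment has no effect.

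The direction follows from the documents. The size does not, because it depends on the share recruited during a pain admission and on the visit rate. Over the assumed grid it runs from about 3% to 51% at 6 months. The result also rests on a pre-treatment window that reaches up to the start of treatment or close to it, which is the natural reading of 6.13.

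It would go too far to infer that every ward recruit contributes an admission and an ED visit, or that the trial's main conclusions are affected. The point concerns one exploratory secondary outcome. It deserves correction because the correction is simple and the bias favours the hypothesis in 2.4.

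**What to change.** In section 6.13:
- Exclude from the pre-treatment count the admission or ED visit during which the family was approached, together with any ED visit linked to it.
- End the 6- and 12-month pre-treatment windows on the day before that index event began. For all other recruits, end them on the day before first contact. Keep their length equal to that of the post-treatment windows. Ending the window on the day before contact would not be enough for ward recruits, because the admission or its ED visit may have started earlier.

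In section 13.4, add recruitment setting (ward, clinic, letter or phone) to the tracking system, which is described only for age, gender and race. Show pre- and post-treatment visits by setting.

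The cost is one extraction rule and one new field, with no change to visits, sample size or treatment. The reported reduction will be less favourable. Events between the end of the pre-treatment window and the start of treatment will fall in neither count and can be listed separately. Some regression to the mean may remain if pain admissions cluster in time; the display by setting would help to show it but cannot remove it.
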